1.3. Schedule of Activities (SoA)

Procedures/ Assessments	Screening	Baseline	Inpatient								Outpatient	EoT	F/U				Comments	
			Dosing												ED			
Visit	1	2	3								4	5	6	7	8	9	10	
Study Day	-28 to -2	-1	1	2	3 ±1	4 ±1	5 ±1	6 ±1	7 ±1	8 ±1	12 ±1	15 ±1	22 ±1	31 ±2	40 ±2	50 ±3	90 ±3	
Week	-4		1	1	1	1	1	1	1	2	2	3	4	5	6	8	12	
Informed consent	X																	
Review/confirm I/E criteria	X			P														
Complete medical history	X																	
Review preexisting conditions/AEs	X	X	P	X	X	X	X	X	X	X	X	X	X	X	X	X	X	AE grading will be via CTCAE version 5.0.
Concomitant medications	X	X	P	X	X	X	X	X	X	X	X	X	X	X	X	X	X	
Substance use (alcohol, tobacco)	X	X																Breath ethanol testing will be performed.
Physical examination	X	X						X							X		X	Complete physical examination will be performed at screening; brief physical examination at other time points. Symptom-directed physical examinations may be conducted at any time, as deemed necessary by the investigator.
Weight	X	X	P										X			X		
Height	X																	

Schedule of Activities (SoA)

Procedures/ Assessments	Screening	Baseline	Inpatient								Outpatient		EoT	F/U				Comments
			Dosing													ED		
Visit	1	2	3								4	5	6	7	8	9	10	
Study Day	-28 to -2	-1	1	2	3 ±1	4 ±1	5 ±1	6 ±1	7 ±1	8 ±1	12 ±1	15 ±1	22 ±1	31 ±2	40 ±2	50 ±3	90 ±3	
Week	-4		1	1	1	1	1	1	1	2	2	3	4	5	6	8	12	
Vital signs (PR, BP)	X	X	X	X	X	X	X	X	X	X	X	X	X	X	X	X	X	
See Section 8.2.2 for details. Vital sign measurements will be measured after at least 5 minutes in the supine position (except body temperature). Blood pressure and heart rate will be collected in triplicate.
 
On days with concurrent ECGs, vital signs, and/or PK sampling, these measurements should occur at approximately the same time. ECGs and vital sign measurements should occur prior to blood draw.
 
Vital sign measurements will be obtained:
 
 • Day 1 at predose (prior to IV or SC dose, but within 90 minutes prior to predose blood draw) • End of infusion (IV group only) • 6 hours after end of infusion (IV group only) • Day 2 (24 hours postdose for IV and SC groups) • Any time for other specified visits (prior to blood draws at same visit).

Schedule of Activities (SoA)

Procedures/ Assessments	Screening	Baseline	Inpatient								Outpatient		EoT	F/U				Comments
			Dosing													ED		
Visit	1	2	3								4	5	6	7	8	9	10	

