1.3.1. Pharmacokinetic and Immunogenicity Sampling

Sample #			Day	Collection Time Point Relative to Ramucirumab Single Dose	Lower Limit For Collection Time	Upper Limit For Collection Time	Pharmacokinetic Analysis Ramucirumab/Placebo		Immunogenicity ADA Assessment
IV	SC	ADA					IV	SC	IV and SC
		1	1	-1 hr ± 5 mins (predose)	-65 mins	-55 mins			X
1			1	1 hr ± 5 mins (end of infusion)	55 mins	65 mins	X		
2			1	4 hrs ± 10 mins	3 hrs 50 mins	4 hrs 10 mins	X		
3	1		1	8 hrs ± 30 mins	7.5 hrs	8.5 hrs	X	X	
4	2		2	24 hrs ± 1 hr	23 hrs	25 hrs	X	X	
5	3		3	48 hrs ± 6 hrs	42 hrs	54 hrs	X	X	
6	4		4	72 hrs ± 6 hrs	66 hrs	78 hrs	X	X	
7	5		5	96 hrs ± 6 hrs	90 hrs	112 hrs	X	X	
8	6		6	120 hrs ± 6 hrs	114 hrs	126 hrs	X	X	
9	7		7	144 hrs ± 6 hrs	138 hrs	150 hrs	X	X	
10	8		8	168 hrs ± 6 hrs	162 hrs	174 hrs	X	X	
	9		12	264 hrs ± 24 hrs	240 hrs	288 hrs		X	
11	10	2	15	336 hrs ± 24 hrs	312 hrs	360 hrs	X	X	X

Sample #			Day	Collection Time Point Relative to Ramucirumab Single Dose	Lower Limit For Collection Time	Upper Limit For Collection Time	Pharmacokinetic Analysis Ramucirumab/Placebo		Immunogenicity ADA Assessment
IV	SC	ADA					IV	SC	IV and SC
	11		22	End of Therapy Visit 504 hrs ± 24 hrs	480 hrs	528 hrs		X	
12	12	3	31	30-day Follow-up	-	-	X	X	X
13	13		40	40 days ± 2 days	-	-	X	X	
14	14		50	50 days ± 3 days	-	-	X	X	
15	15	4	90	90 days ± 3 days ~ 12 weeks	-	-	X	X	X

Abbreviations: ADA = antidrug antibody; IV = intravenous; SC = subcutaneous.

The actual date and exact 24-hour clock time of sample collection should be recorded on the requisition form. Samples are requested to be taken at the specified time; however, aberrations to the specified sampling times will not be considered protocol deviations as long as the samples are taken and the actual sampling time is recorded. It is essential that the actual times of doses and samples are recorded accurately on the appropriate forms.

2. Introduction

Ramucirumab is a human receptor-targeted monoclonal antibody (mAb) that specifically binds vascular endothelial growth factor (VEGF) receptor 2. Ramucirumab has been marketed worldwide as an intravenous (IV) formulation since 2014 and is well-established treatment, as a single agent and/or in combination with chemotherapy, for the following second-line indications:

- gastric or gastroesophageal junction (GEJ) adenocarcinoma
- non-small cell lung cancer (NSCLC)
- colorectal cancer (CRC), and
- hepatocellular carcinoma (HCC)

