 - administered at a concentration of 175 mg/mL as 2×2-mL injections.

- **Group 3 will test a ramucirumab IV dose (maximum of 350 mg)**
 - administered as a 60-minute infusion (maximum 35 mL×10 mg/mL).
 - Analysis of safety and PK data from Groups 1 to 3 will allow initiation of Group 6.
- **Group 4 will test a ramucirumab 350-mg SC dose**
 - administered at a concentration of 87.5 mg/mL as 2×2-mL injections
 - The purpose is to investigate the effect of a different drug product concentration on PK and safety and Group 1 will be the reference comparison group.
- **Group 5 will test a ramucirumab 350-mg SC dose**
 - administered at a concentration of 175 mg/mL as 2×1-mL injections
 - The purpose is to investigate the effect of a different volume administered at the injection site on PK and safety and Group 1 will be the reference comparison group.
- **Optional Group 6 may test SC ramucirumab dose, maximum 350 mg, to further understand SC ramucirumab PK and safety in healthy participants**
 - administered at a concentration of 175 mg/mL administered via an infusion pump according to the pharmacy manual.

The SC injection site will be the abdomen. See Section 6.1 for details.

Following the safety review of Groups 1 and 2, the sponsor and investigator agreed to allow doses to be reduced for remaining groups. This may mean that less groups may need to be studied. The asymptomatic transaminase increases observed during the safety review have also lead to a change in the exclusion criteria to further enhance safety of the participants. In view of these findings, subsequent doses will be capped at 350 mg. Lower doses may also be studied. These decisions will be based on emerging data (see Section 4.3 for further details).

Injection site pain (ISP) and ISRs will be monitored in each group, and a comparison of scorings will be used. The severity of ISP and ISRs reported across all participants will be evaluated. The data from Group 1, in comparison to Groups 4 and 5, will provide insight about the effect of injection volumes and ramucirumab concentration on ISP and ISR.

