6.1. Study Intervention(s) Administered

Intervention Name	Ramucirumab IV (marketed IV formulation)	Ramucirumab SC	Placebo for SC	Placebo for IV
Type	Drug	Drug	Matching placebo	Matching placebo
Dose Formulation	Vial	Vial	Vial	Vial
Unit Dose Strength(s) ^a	Experimental	Experimental	Placebo	Placebo
Dosage Level(s) ^a	350 mg	350 or 700 mg	NA	NA
Route of Administration ^a	IV infusion (Group 3)	SC injection (Groups 1, 2, 4, 5) SC infusion with a pump (Group 6)	SC injection (Groups 1, 2, 4, 5) SC infusion with a pump (Group 6)	IV infusion (Group 3)
Use ^a	Experimental	Experimental	Placebo	Placebo
IMP and NIMP ^a	IMP	IMP	NIMP	NIMP
Sourcing ^a	Provided centrally by the sponsor	Provided centrally by the sponsor	Provided centrally by the sponsor	Provided centrally by the sponsor
Packaging and Labeling ^a	Study intervention will be provided in a vial. Each vial will be labeled as required per country requirement.	Study intervention will be provided in a vial. Each vial will be labeled as required per country requirement.	Placebo will be provided in a vial. Each vial will be labeled as required per country requirement.	Placebo will be provided in a vial. Each vial will be labeled as required per country requirement.
Current/Former Names or Aliases ^a	Ramucirumab, Cyramza®, LY3009806	Ramucirumab, Cyramza®, LY3009806	Placebo	Placebo

Abbreviations: IMP = investigational medicinal product; IV = intravenous; NA = not applicable;

NIMP = noninvestigational medicinal product; SC = subcutaneous.

a Information provided in this table (dose formulation, sourcing, packaging and labeling, current/former names or aliases) may change throughout the study or may vary by country.

The study intervention will be administered as a slow, IV infusion over at least 60 minutes in Group 3; and as an SC infusion (with a pump) in Group 6 per pharmacy manual; or SC injection in Groups 1, 2, 4, and 5. Sites must have resuscitation equipment, emergency drugs, and appropriately trained staff available during the IV or SC infusion/SC injection and for at least 1 hour after participants have completed the IV or SC infusion/SC injection.

The SC injection site will be the abdomen. The study intervention will be given in the CRU by qualified CRU personnel as designated by the investigator. Study injections should be given by a

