### **General PK Parameter Rules**

- Actual sampling times will be used in the final analyses of individual PK parameters, except for non-bolus pre-dose sampling times which will be set to zero.
- $C_{\max}$  and  $t_{\max}$  will be reported from observed values. If  $C_{\max}$  occurs at more than one time point,  $t_{\max}$  will be assigned to the first occurrence of  $C_{\max}$ .
- AUC parameters will be calculated using a combination of the linear and logarithmic trapezoidal methods (linear-log trapezoidal rule). The linear trapezoidal method will be applied up to  $t_{\max}$  and then the logarithmic trapezoidal method will be used after  $t_{\max}$ . The minimum requirement for the calculation of AUC will be the inclusion of at least three consecutive concentrations above the lower limit of quantification, with at least one of these concentrations following  $C_{\max}$ .
- AUC( $0-\infty$ ) values where the percentage of the total area extrapolated is more than 20% will be flagged. Any AUC( $0-\infty$ ) value excluded from summary statistics will be noted in the footnote of the summary table.
- Half-life ( $t_{1/2}$ ) will be calculated, when appropriate, based on the apparent terminal log-linear portion of the concentration-time curve. The start of the terminal elimination phase for each participant will be defined by visual inspection and generally will be the first point at which there is no systematic deviation from the log-linear decline in plasma concentrations. Half-life will only be calculated when a reliable estimate for this parameter can be obtained comprising of at least 3 data points. If  $t_{1/2}$  is estimated over a time window of less than 2 half-lives, the values will be flagged in the data listings. Any  $t_{1/2}$  value excluded from summary statistics will be documented in the footnote of the summary table.
- A uniform weighting scheme will be used in the regression analysis of the terminal log-linear portion of the concentration-time curve.
- The parameters based on observed last quantifiable drug concentration will be reported.

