### **Average Concentration vs. Time Profiles**

- The average concentration profiles will be graphed using scheduled (nominal) sampling times.
- The average concentration profiles will be graphed using arithmetic average concentrations.
- The pre-dose average concentration for single-dose data from non-endogenous compounds will be set to zero. Otherwise, only quantifiable concentrations will be used to calculate average concentrations.
- Concentrations at a sampling time outside sampling time window specified in Section 1.3.1 in the protocol, or  $\pm 10\%$ , will be excluded from the average concentration profiles.
- Concentrations excluded from the mean calculation will be documented in the CSR.
- A concentration average will be plotted for a given sampling time only if 2/3 of the individual data at the time point have quantifiable measurements that are within the sampling time window specified in the protocol or  $\pm 10\%$ . An average concentration estimated with less than 2/3 but more than 3 data points may be displayed on the mean concentration plot if determined to be appropriate and will be documented within the CSR.

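### The window for the IV end-of-infusion PK sample opens before the infusion ends, so a permitted draw can move observed IV tmax to 4 h and lower observed Cmax by up to about 5%

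*Protocol*

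**What the plan says.** Protocol Section 1.3.1 times its samples under the column heading "Collection Time Point Relative to Ramucirumab Single Dose". The first IV row is "1 hr ± 5 mins (end of infusion"), with printed limits of 55 and 65 minutes. The next IV sample is at 4 h ± 10 min. A note under the table says that "aberrations to the specified sampling times will not be considered protocol deviations", provided the sample is taken and its actual time recorded.

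On infusion length, Section 6.1 states: "The study intervention will be administered as a slow, IV infusion over at least 60 minutes in Group 3". It gives no maximum. Section 4.1 describes the dose as "administered as a 60-minute infusion (maximum 35 mL×10 mg/mL"), and the synopsis, Section 4.3 and SAP Section 5 also give 60 minutes.

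For visits with concurrent measurements, the Schedule of Activities says "ECGs and vital sign measurements should occur prior to blood draw". Protocol Sections 8.2.2 and 8.2.3 repeat that order. The IV group has vital signs and an ECG at the end of infusion.

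In SAP Section 9.3.1, Cmax and tmax "will be reported from observed values", while individual parameters use actual sampling times. For the average profiles only, the SAP excludes "Concentrations at a sampling time outside sampling time window specified in Section 1.3.1 in the protocol" or beyond ±10%. IV Cmax and tmax are listed among the primary PK endpoints (protocol Section 3, SAP Section 4.1).

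**The concern.** During a constant-rate infusion the concentration rises until the infusion stops. A sample meant to catch the peak must therefore not be drawn before the stop. The 1.3.1 row is labelled as end of infusion, but its limits are set on a clock that starts at dosing. The clock and the event coincide only if the infusion ends at or before the moment of the draw.

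No IV sample lies between this one and 4 h, and the SAP does not interpolate to the end of infusion. Recording the true draw time keeps AUC right but cannot restore a peak that was not sampled. Two primary PK descriptors of the IV group, Cmax and tmax, depend on that one draw. With 7 active IV participants, the median tmax is the fourth ordered value, so four early draws would be enough to move it from about 1 h to about 4 h.

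**Working it through.** **1. The plan's window.** 60 − 5 = 55 min and 60 + 5 = 65 min, as printed. Because the row places the end of infusion at 1 h, time zero is the start of infusion.

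**2. Window against infusion length.** For a 60-min infusion, any draw from 55 min to just under 60 min precedes the end. For an infusion longer than 65 min, the whole window does. The documents give no maximum duration, so lengths above 60 min are assumptions used to show a range.

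**3. Model inputs (protocol Section 2.1).** Distribution half-life about 20 h; elimination half-life about 10 days to 2 weeks; a 2-fold fall over about the first 3 days.

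- α = ln 2 / 20 = 0.0347 per h
- β = ln 2 / (24 × 10) = 0.00289 per h, down to ln 2 / (24 × 14) = 0.00206 per h
- Weight A is set so that C(72 h)/C(0) = 0.5: A = (e^(−72β) − 0.5) / (e^(−72β) − e^(−72α))
- 10 days: (0.8123 − 0.5) / (0.8123 − 0.0825) = 0.428
- 14 days: (0.8620 − 0.5) / (0.8620 − 0.0825) = 0.464

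For an infusion of length T, C(t) is proportional to A·g(α) + (1 − A)·g(β), where g(k) = [1 − e^(−k·min(t,T))] / (kT) × e^(−k·max(t−T,0)).

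**4. Concentration as a percentage of the true end-of-infusion peak** (ranges cover elimination half-lives of 10 to 14 days):

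| Infusion length | Draw at 55 min | 60 min | 65 min | 4-h sample |
|---|---|---|---|---|
| 60 min | 91.7 | 100 | 99.9 | 95.1–95.3 |
| 65 min (assumed) | 84.7 | 92.4 | 100 | 95.3–95.4 |
| 70 min (assumed) | 78.7 | 85.8 | 92.9 | 95.4–95.6 |
| 75 min (assumed) | 73.5 | 80.2 | 86.8 | 95.5–95.7 |

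Observed Cmax is the larger of the early draw and the 4-h value. The 4-h sample therefore limits the loss to about 5%, but where it is the larger value, tmax is reported as 4 h.

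**5. Where tmax switches.** For a 60-min infusion, the early draw falls below the 4-h value when taken before about 57 min. The latest permitted draw, at 65 min, falls below the 4-h value once the infusion lasts about 68 min or more (95.6% against 95.3–95.5% at 68 min).

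**6. AUC(0–∞).** With the linear-log rule, a 55-min draw in a 60-min infusion gives an AUC ratio of 0.9994–0.9995 against a draw at the end of infusion. A 55-min draw in an assumed 90-min infusion gives 0.9977–0.9982. The effect is about 0.2% or less.

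**7. Average-profile rule.** ±10% of 60 min is 54 to 66 min. A correct end-of-infusion draw after an assumed 70-min infusion lies outside both this range and 55–65 min, so it is excluded. A 55-min draw, taken during the infusion, is kept.

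**8. The 96-h row.** 96 + 6 = 102 h, but the printed upper limit is 112 h. The neighbouring ±6 h rows add correctly (72 + 6 = 78; 120 + 6 = 126).

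**The case against.** The strongest reply is that a site following the protocol would usually draw late, not early. The row is labelled as end of infusion, off-time draws are not deviations, and Section 8.5 allows timing to be altered to come closer to the peak. Vital signs and ECG are due at the end of infusion and must come before blood is taken, which tends to push the draw past the stop. A late draw costs little: 15 min after the end still reads 99.6% of peak in the same model. This stands, and it rules out saying that the sample is fixed before the end of infusion. But nothing requires the site to wait, the printed lower limit is 55 min, and the average-profile rule would count against a site that waited through a longer infusion.

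Most passages say 60 minutes and only Section 6.1 says at least 60, so the long-infusion rows in the table are hypothetical. That also stands. The defect at exactly 60 minutes remains.

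A reader might infer that the comparison of SC with IV exposure is compromised. The documents do not support that:

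- Bioavailability uses AUC(0–∞). The planned Cmax and tmax comparisons in SAP Section 9.3.2 are among SC groups.
- The aim of a lower Cmax refers to 10 mg/kg every 2 weeks IV, not to this IV group of at most 350 mg.
- Appendix 6 gives IV Cmax of 206 µg/mL (5th–95th percentile 153–285), a CV of about ln(285/153) / (2 × 1.645) = 19%. With 7 participants the standard error is about 19/√7 = 7%, larger than the worst-case 5%.

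A reader might also take the 80–92% values as the reported Cmax. They are single-sample values; the 4-h sample replaces them.

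Finally, assay noise can move tmax by itself. If independent assay CVs of 5–10% are assumed (not in the documents), about 24–36% of perfectly timed 60-min profiles would still show tmax at 4 h. The change proposed here would not prevent that.

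**Conclusion.** The inconsistency is real: Section 1.3.1 permits the end-of-infusion sample to be taken before the infusion has ended, even when it lasts exactly 60 minutes. The main effect is on tmax, which can move from about 1 h to 4 h. Observed IV Cmax can be understated by up to about 5%. AUC and bioavailability are essentially untouched.

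The sizes rest on approximate half-lives established in cancer patients, on a constant infusion rate and, for the 68-minute threshold, on an assumed infusion length. How many draws would in practice fall before the stop cannot be judged from the documents.

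The 112-h limit is a separate, minor slip. A reader might think it alters the PK parameters, but these use actual times, so only the average profiles are exposed. The point is worth correcting because the remedy is nearly free. It is not a threat to the study's conclusions.

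**What to change.** - In Section 1.3.1, define IV sample 1 by the recorded actual end of infusion, with no lower limit before it and a short upper limit after it. For example, 0 to +15 min reads at least about 99.6% of peak in the model and leaves room for the end-of-infusion vital signs and ECG first. Their order before the draw is then kept, and Sections 8.2.2 and 8.2.3 need no exception. State that infusion start and stop times are recorded.
- In SAP Section 9.3.1, apply the average-profile window for this sample to the event-based time.
- Reconcile the passages giving 60 minutes with the one giving at least 60 minutes. This review takes no position on which is right.
- Correct the upper limit of the 96-h row from 112 to 102 hours.

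The cost is a few wording changes and no extra sample, ideally before Group 3 is dosed. The small downside is that the nominal time of this sample will vary with infusion length. If Group 3 has already been dosed, list each draw time against the recorded infusion stop time and flag Cmax and tmax where the draw came first.
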